### 7.3 Efficacy Analysis Set

The efficacy analysis set will be used for secondary endpoints. The efficacy analysis set includes all enrolled subjects in Study 20140159 who received at least one dose of cinacalcet during Study 20140159 and have at least one assessment

after Study Day 1. Subjects will be analyzed according to the treatment received in the parent studies and overall.

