**7.4 Study 20130356 SOC Set**

The Study 20130356 SOC set will be used for secondary endpoints that analyze subjects from Study 20130356 SOC arm only. The Study 20130356 SOC set includes all Study 20140159 enrolled subjects from Study 20130356 who did not receive cinacalcet prior to Study Day 1 of 20140159 and received at least one dose of cinacalcet in Study 20140159 and have at least one assessment after Study Day 1 of 20140159.

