**Sensitivity analyses to assess the effect of missing data or non-compliance**

**Secondary endpoints for Study 20140159 only**

Secondary endpoint	Sensitivity Analyses	Planned for Interim or Final analysis
Achievement of $\geq 30\%$ reduction from baseline to mean iPTH during weeks 11 and 15 (SOC arm of Study 20130356 only)	
Inverse Probability Weighting (IPW) The missingness model will include study baseline iPTH, cCa, phosphorus, age group, sex, race, and AEs of nausea, vomiting and symptomatic hypocalcemia. Dialysis vintage, AE or IPD related to ending IP may be also included in the model depending on the EOIP reason observed in the study.
 
The final weighted pooled logistic regression model will include study baseline iPTH, cCa, phosphorus and age group. This analysis will be performed using the Study 20130356 SOC set.
	Final analysis only
	
Completer analysis: Only subjects completing 15 weeks of study in the Study 20130356 SOC set will be included in the analysis.
 
Subjects with no iPTH values during weeks 11 and 15 will be considered as nonresponders.
	Final analysis only
	
Per protocol analysis: Subjects in per protocol set who did not receive cinacalcet in the parent study and have at least one iPTH value during weeks 11 and 15 will be used.
	Interim and Final analyses
	
Nearest 2 imputation If no values are observed during weeks 11 and 15, the nearest two values at or after week 7 will be used, including unscheduled visit values, values prior to or after weeks 11 and 15. Subjects with no observed values at or after week 7 will be considered nonresponders.
	Final analysis only

Page 1 of 3

Secondary endpoints for Study 20140159 only

Secondary endpoint	Sensitivity Analyses	Planned for Interim or Final analysis
Achievement of $\geq 30\%$ reduction from baseline to mean iPTH during weeks 23 and 28 (SOC arm of Study 20130356 only)	IPW:  The IPW method is same as specified for the sensitivity of binary endpoint "Achievement of $\geq 30\%$ reduction from study baseline to mean iPTH during weeks 11 and 15".	Final analysis only
Achievement of a mean iPTH value $\leq 300$ pg/mL during week 23 and 28 (efficacy analysis set)	Completer analysis:  Only subjects with at least one iPTH value during week 23-28 will be included in the analysis.	Final analysis only

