	Per protocol analysis:  Subjects from in per protocol set for Study 20140159 only who did not receive cinacalcet in the parent study and have at least one iPTH value during weeks 23 and 28 will be used for the endpoint defined for SOC arm of Study 20130356 only.  Subjects from the per protocol set for Study 20140159 only and with at least one iPTH value during weeks 23 and 28 will be used for the other endpoint.	Interim and Final analyses

Page 2 of 3

Secondary endpoints for Study 20140159 only

Secondary endpoint	Sensitivity Analyses	Planned for Interim or Final analysis
Percent change from baseline to mean iPTH during weeks 23 and 28 (SOC arm of Study 20130356 only)	Repeated measures mixed effect model:  The repeated measures model will include treatment group, study baseline age group, scheduled visits, and interaction of treatment group and scheduled visits. An unstructured covariance will be used for the model.	Final analysis only
Change in corrected total serum calcium from baseline to mean value during week 23 and 28 (efficacy analysis set)	Completer analysis:  Only subjects with at least one required lab value for the endpoint during week 23-28 will be included in the analysis.	Final analysis only
Change in serum phosphorus from baseline to mean value during week 23 and 28 (efficacy analysis set)	Per protocol analysis:  Subjects in both the Study 20130356 SOC set and per protocol set for Study 20140159 only and with at least one iPTH value during weeks 23 and 28 will be used for the endpoint defined for SOC arm of Study 20130356 only.  Subjects from the per protocol set for Study 20140159 only and with at least one corresponding lab value during weeks 23 and 28 will be used for other endpoints.	Interim and Final analyses

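### The repeated-measures sensitivity model in SAP 10.6.2 omits the study baseline value of the outcome and, for the SOC-only iPTH endpoint, carries redundant treatment terms

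*SAP*

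**What the plan says.** The first sensitivity table in SAP 10.6.2 (endpoints for Study 20140159 only) groups three continuous endpoints: percent change in iPTH for the former SOC arm, and change in corrected calcium and in phosphorus for the Efficacy Analysis Set. All run from study baseline to the mean over weeks 23 and 28. The mixed model, planned for the final analysis only, reads: "The repeated measures model will include treatment group, study baseline age group, scheduled visits, and interaction of treatment group and scheduled visits". The next sentence is: "An unstructured covariance will be used for the model". Completer and per-protocol analyses are the only other sensitivity analyses for these endpoints.

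SAP 7.4 defines the set that "will be used for secondary endpoints that analyze subjects from Study 20130356 SOC arm only". It consists of "enrolled subjects from Study 20130356 who did not receive cinacalcet prior to Study Day 1 of 20140159", who were then dosed and assessed in the extension. Treatment group means parent-study treatment. SAP 7.3 states: "Subjects will be analyzed according to the treatment received in the parent studies and overall".

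For the binary iPTH endpoints, the same section plans inverse probability weighting (IPW). Its missingness model includes baseline iPTH, calcium and phosphorus, and so does its outcome model: "The final weighted pooled logistic regression model will include study baseline iPTH, cCa, phosphorus and age group".

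SAP 10.6.1 handles missing weeks 23 and 28 values in the main analysis with the mean of the last two post-baseline values from the titration phase. SAP 10.1 drops laboratory values taken more than 7 days after the last dose, so stopping treatment creates missing data. SAP 5 and 10.1 state that there is no formal testing.

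**The concern.** A mixed model serves as a missing-data check because it uses observed information to stand in for values lost after dropout. It is valid if missingness depends only on what the model contains. With baseline left out, the only information it has on a subject who drops out is age group, parent treatment (where that varies) and whatever post-baseline values were seen first. If subjects with high or low baseline values stop early and also respond differently, part of the distortion stays in the estimate.

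The omission also sits oddly with the rest of the section. The SAP treats baseline laboratory values as relevant to both missingness and response for the binary iPTH endpoints, but plans no weighting for the continuous ones. The completer and per-protocol analyses keep only subjects with data in the window. The mixed model is therefore the only sensitivity analysis of these endpoints that tries to correct for missing data.

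The treatment-group terms raise a separate and smaller question. Every subject in the SOC Set has the same parent treatment, so the model cannot be fitted literally for iPTH and the programmer must decide what to do.

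**Working it through.** The plan attaches no figure to this model, so there is none to reproduce. Two checks were made.

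**1. Treatment terms in the SOC Set**

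Inputs: about 24 SOC subjects (Protocol 2.5.1: approximately 48 randomised 1:1, 48 / 2 = 24; the number rolling over is not given) and 7 on-treatment iPTH visits (weeks 3, 7, 11, 15, 19, 23 and 28).

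- Without treatment terms: intercept 1 + age group 1 + visits 7 = 9 columns, rank 8.
- As written: 9 + treatment group 1 + treatment-by-visit 7 = 17 columns, rank still 8.
- Largest difference in fitted values: 4e-16, which is rounding error.

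The extra terms are not estimable, and they do not alter the estimated mean.

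**2. Omitting baseline**

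The quantity is the mean percent change in iPTH over weeks 23 and 28. It was estimated by maximum likelihood, equivalent to the unstructured model under monotone dropout, with and without baseline. None of the following assumptions comes from the documents:

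- SD 40 points
- correlation of baseline with percent change 0, -0.3 or -0.5, equal at every visit
- adjacent-visit residual correlation 0.71 or 0.89
- dropout 20% or 40%, after week 3 and before week 23
- log-odds of dropout 1 or 2 per SD of baseline.

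Large-sample bias without baseline, in percentage points:

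| Baseline correlation | Adjacent-visit correlation | 20%, log-odds 1 | 20%, log-odds 2 | 40%, log-odds 1 | 40%, log-odds 2 |
|---|---|---|---|---|---|
| -0.3 | 0.71 | 1.22 | 1.85 | 2.21 | 3.22 |
| -0.3 | 0.89 | 0.59 | 0.86 | 1.02 | 1.55 |
| -0.5 | 0.71 | 1.60 | 2.46 | 2.98 | 4.55 |
| -0.5 | 0.89 | 0.80 | 1.22 | 1.49 | 2.19 |

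- With baseline fitted, the bias is within 0.06 in all these settings.
- With zero baseline correlation, it is within 0.11 of zero either way.
- Restricting to completers gives 2.1 to 9.8 points in the same settings, so the model as written already removes part of the bias.
- A second simulation (24 subjects, 27% dropout, SD about 30, correlation 0.3 to 0.5) gave 0.5 to 1.9 points without baseline and 0.1 or less with it.

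Together the range is roughly 0.5 to 4.6 points. The positive sign means that the fall in iPTH is understated. It follows from assuming that high-baseline subjects both respond more and drop out more; reversing one of these reverses the sign.

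**3. Which form of adjustment, at 24 subjects**

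*Baseline-by-visit* (correlation -0.5, adjacent-visit correlation 0.71, 40% dropout, log-odds 1). Error is measured against the mean the same subjects would have given with complete data.

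- Bias goes from 2.86 to -0.04 and the SD of the error from 7.83 to 10.2.
- Root-mean-square error = sqrt(bias² + SD²). Without baseline: sqrt(2.86² + 7.83²) = 8.3. With baseline-by-visit: sqrt(0.04² + 10.2²) = 10.2.
- Across 16 settings at 24 subjects, root-mean-square error was higher with baseline-by-visit in all 16 (for example 6.9 against 7.2, and 10.8 against 13.0).

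*One common baseline slope* (SD 40, correlation -0.3, dropout 27% to 40%).

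- The estimate moves 0.8 to 3.0 points in the direction that removes the bias.
- Root-mean-square errors with and without the term pair as 8.6 and 8.9, 10.9 and 10.5, 10.8 and 10.6, 8.6 and 8.8, 10.1 and 10.0. No pair differs by more than 0.4.
- A smaller check (240 to 250 runs in each of three settings, Monte Carlo error about 0.5) found shifts of 1.0 to 1.4, with the SD of the error going from 8.4 to 8.4, 8.9 to 8.9 and 8.2 to 8.3.

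The bias is thus reduced at essentially no cost in precision.

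**The case against.** The strongest case against runs as follows. The treatment terms do no harm. Baseline-related dropout is already addressed by IPW for the binary iPTH endpoints, one of them over the same weeks 23 and 28. Percent change is already scaled to baseline. Earlier post-baseline values protect the mixed model in part. Every number above rests on assumed inputs. The analysis is a final-analysis sensitivity check on secondary endpoints in a study without testing.

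Most of this stands and limits the point, but it does not remove it. IPW on a responder proportion says nothing about the mean change, and calcium and phosphorus have no IPW analysis at all. Scaling by baseline does not make percent change independent of baseline, and calcium and phosphorus are analysed as absolute changes.

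That one model serves three endpoints is a reading of a table flattened from PDF, in which the model text sits beside the iPTH row. The per-protocol text supports that reading: it sits beside phosphorus, yet gives separate instructions for the SOC-only endpoint and for the others, so the cells appear to be shared.

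A reader might go further in three ways that the documents do not support:

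- **That the iPTH model is wrong because of its treatment terms.** They are redundant, and the fit is identical without them.
- **That baseline is known to predict dropout here.** No correlation or dropout rate is given. The SAP's IPW model only treats it as plausible.
- **That an unstructured covariance cannot be fitted.** Seven visits need 7 × 8 / 2 = 28 covariance parameters, which is demanding for about 24 subjects, but no failure has been shown. The figure of 24 is itself approximate, since the protocol says approximately 48 and gives no roll-over number.

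**Conclusion.** The point holds as a low-cost improvement. The mixed model omits the study baseline value of the outcome, which the trial already collects and which the SAP uses in its IPW models. If dropout is related to baseline and baseline to response, the modelled mean percent change in iPTH at weeks 23 and 28 is biased by roughly 0.5 to 4.6 percentage points; if baseline is unrelated to response, by about zero. Both conditions, and the SDs, correlations and dropout rates behind the range, are assumptions. The bias for calcium and phosphorus was not computed. For the SOC-only iPTH endpoint the treatment terms are redundant but harmless, and they are meaningful for the other two endpoints.

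A reader might also infer that the fullest adjustment, baseline-by-visit, should be required. The calculations argue against that at about 24 subjects: it costs more precision than the bias it removes. No error rate, sample size or main analysis is affected.

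**What to change.** In the mixed-model entry of SAP 10.6.2:

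1. Add the study baseline value of the outcome (iPTH, corrected calcium or phosphorus) as a main effect with one common slope, in the model for each of the three endpoints. Evaluate the modelled means at the average baseline of all subjects in the set being summarised, including those who drop out.
2. For the SOC Set, state the iPTH model separately: visit, age group and baseline iPTH, with no treatment group and no treatment-by-visit term. Keep those terms for calcium and phosphorus.
3. Do not require baseline-by-visit. If the baseline effect differs between visits, the common slope will remove only part of the bias, which is acceptable at this sample size.
4. Optionally, name a fallback covariance structure in case the unstructured fit does not converge.

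The cost is a few lines of SAP wording. SAP 6.3 already defines the baseline values as the mean of the screening and pre-dose Study Day 1 samples, so no new data are needed.

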**Secondary endpoints for combined 20130356, 20110100 and 20140159 studies**

Secondary endpoint	Sensitivity Analyses	Planned for Interim or Final analysis
Achievement of $\geq 30\%$ reduction from day 1 of cinacalcet treatment to mean iPTH during weeks 11 and 15	IPW:  The missingness model will include baseline iPTH, cCa, phosphorus, age group at first cinacalcet dose, sex, race, and AEs of nausea, vomiting and symptomatic hypocalcemia. Dialysis vintage, AE or IPD related to ending IP may be also included in the model depending on the EOIP reason observed in the study.  Completer analysis:  Only enrolled subjects who completed 15 weeks from Day 1 of cinacalcet treatment will be included in the analysis. Subjects with no iPTH values during weeks 11 and 15 since Day 1 of cinacalcet treatment will be considered as nonresponders.	Final analysis only
	Per protocol analysis:  Subjects from the per protocol set for combined 20130356, 20110100 and 20140159 studies and with at least one iPTH value during weeks 11 and 15 will be used.	Final analysis only
	Nearest 2 imputation  If no values are observed during weeks 11 and 15 from Day 1 of cinacalcet treatment, the nearest two values at or after week 7 from Day 1 of cinacalcet treatment will be used, including unscheduled visit values, values prior to or after weeks 11 and 15. Subjects with no observed values at or after week 7 will be considered nonresponders.	Final analysis only

**Secondary endpoints for combined 20130356, 20110100 and 20140159 studies**

Secondary endpoint	Sensitivity Analyses	Planned for Interim or Final analysis
Achievement of $\geq 30\%$ reduction from day 1 of cinacalcet treatment to mean iPTH during weeks 23 and 28	IPW: The IPW method is same as specified for the sensitivity of binary endpoint "Achievement of $\geq 30\%$ reduction from day 1 of cinacalcet treatment to mean iPTH during weeks 11 and 15	Final analysis only
	Completer analysis: Only subjects with at least one iPTH value during week 23-28 since Day 1 of cinacalcet treatment will be included in the analysis.	Final analysis only
	Per protocol analysis: Subjects from the per protocol set for combined 20130356, 20110100 and 20140159 studies and with at least one iPTH value during weeks 23 and 28 will be used.	Final analysis only

Page 2 of 2

**10.6.3 Analyses of Exploratory Endpoints**

**20140159 study only**

**Analyses of exploratory endpoints will be based on Efficacy Analysis Set.** Growth velocity and change in Tanner stage from **Study Day 1 in study 20140159 to end of study** will be summarized using descriptive statistics. **The analysis will only include subjects who have growth velocity values available or tanner stage assessments available at both Study Day 1 in study 20140159 and end of study; no imputation will be done for missing values.**

**Actual values, change and percent change of iPTH, serum cCa, serum phosphorus and CaxP values at scheduled visits from study baseline for all Efficacy Analysis Set subjects through last dose of IP+7 days will be summarized and presented graphically.**

**20130356, 20140159 and 20110100 studies combined**

**Summary statistics of the exploratory endpoints will also be presented from day 1 of cinacalcet treatment through end of study of 20140159.**

**The analysis will only include subjects who have growth velocity values available and Tanner stage assessments available at both day 1 of cinacalcet treatment and end of study; no imputation will be done for missing values.**

**Actual values, change and percent change of iPTH, serum cCa, serum phosphorus and CaxP values at scheduled visits from baseline at first cinacalcet dose for all Efficacy Analysis Set subjects through last dose of IP+7 days will be summarized and presented graphically.**

#### **10.7 Safety Analyses**

**The Safety Analysis Set is used for all analyses specified in this section unless otherwise specified.**

##### **10.7.1 Adverse Events**

The Medical Dictionary for Regulatory Activities (MedDRA) version 17.0 or later will be used to code all adverse events (AE) to a system organ class and a preferred term. All adverse event tables will be summarized.

##### **20140159studyonly**

An overall summary of treatment-emergent adverse events, **defined for study 20140159 only in section 6.4**, by toxicity grade and type will be provided.

Subject incidence of all treatment-emergent AEs, serious AEs, treatment-related, serious treatment-related AEs, AEs leading to withdrawal of investigational product, and fatal AEs will be tabulated by system organ class in alphabetical order and preferred term in descending order of frequency.

Subject incidence of AEs will be summarized for all treatment-emergent AEs, serious AEs, and EOIs by preferred term in descending order of frequency.

Subgroup analyses **of age groups** will be presented by system organ class in **alphabetical order** and preferred term in descending order of frequency if there are more than 4 subjects in each subgroup.

Treatment-emergent AEs will be listed for subjects who experienced QTcB  $\geq$  500 msec on study.

Focused adverse events questionnaires were administered for events of hypocalcemia, seizure, and infection, of which subject incidence will also be summarized.

**Combined20130356, 20140159and20110100studies**

**Subject follow-up time adjusted incidence of all treatment-emergent AEs and EOIs, defined for studies 20130356, 20140159 and 20110100 combined in section 6.4, will also be tabulated by preferred term in descending order of follow-up time adjusted incidence rates for all subjects.**

**10.7.2 Laboratory Test Results**

**All laboratory test results in 20140159 study only and combined with parent studies will be summarized by treatment received in parent studies and overall.**

**20140159studyonly**

Descriptive statistics for actual values, changes, and percent changes from **study** baseline of selected laboratory parameters below will be presented at **scheduled visits** during the study. In addition, shift tables will summarize toxicity grades using CTCAE (version 3) by worst increase and decrease between **study** baseline and any visit up to the end of the study for selected laboratory parameters below.

	Summary over time	Shifts in grade from study baseline
Serum Chemistry		
Albumin	X	one way shift (decreased)
Bicarbonate	X	
Blood Urea Nitrogen	X	
Chloride	X	
Creatinine	X	
Potassium		two-way shift
Sodium		two-way shift
Total Protein		
Liver function test		
ALT		one way shift (increase )
AST		one way shift (increase )
Total Bilirubin		one way shift (increase )
Alk Phos		one way shift (increase )

Page 1 of 2

	Summary over time	Shifts in grade from study baseline
Hematology		
Platelets		one way shift (decrease )
Hemoglobin	x	one way shift (decrease )
White blood cell count		one way shift (decrease )
Red blood cell count		
Other		
iPTH	x	
Corrected Ca	x	two-way shift
Ionized Ca	x	two-way shift
Phosphorus	x	
Ca x P	x	
BALP, NTx, CTx, P1NP (For 20140159 subjects from parent Study 20130356 only)	x	
FGF 23 (For 20140159 subjects from parent Study 20130356 only)	x	
25(OH)D (For 20140159 subjects from parent Study 20130356 only)	x	
Total and bioavailable testosterone (male)	x	

Page 2 of 2

Subject incidence of corrected total serum calcium value < 8.4 mg/dL, <8.0 mg/dL, <7.5 mg/dL or ionized calcium value < 1.05 mmol/L, <1.00 mmol/L and <0.94 mmol/L respectively **during study 20140159** will also be summarized.

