# 4. SUBJECT ELIGIBILITY

Before any study-specific activities/procedure, written informed consent must be obtained (see Section 11.1). In addition to written informed consent from a legally acceptable representative, the assent of the child also must be obtained, as appropriate and if requested by the institutional review board/independent ethics committee (IRB/IEC).

Subjects from the cinacalcet arm of Study 20130356 or subjects in Study 20110100 who had their dose withheld at the EOIP visit, may enroll in this study if they meet eligibility criteria but will not restart dosing until the criteria for restarting dosing, defined in Section 6.2.3, are met.

Subjects who were  $\leq$  18 years old at week 20 in the 20130356 study or at the time of study termination, are eligible to enter this Study 20140159 even if they have already turned 18 years of age or are due to turn 18 years of age during their planned participation in the 20140159 study.

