#### Subjects Randomized to the 20130356 Standard of Care Arm Only

- iPTH value  $\geq$  300 pg/mL (within 7 days of day 1 in Study 20140159)
- 107 Corrected calcium value ≥ 8.8 mg/dL within 7 days of day 1 in Study 20140159

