#### Laboratory Data, Blood Pressure, and Heart Rate

Descriptive statistics for values, changes and percent changes of selected laboratory parameters from first dose of IP date will be presented at each measurement time point during the study. In addition, shift tables will summarize grades using CTCAE (version 3) by worst grades between baseline and any visit up to the end of the study for selected hematology and chemistry parameters.

The incidence of hypocalcemia after the first dose of IP will be summarized using descriptive statistics. Hypocalcemia will be defined in two ways: with the subject incidence of corrected serum calcium of < 7.5 mg/dL, < 8.0 mg/dL, and < 8.4 mg/dL being summarized; and with subject incidence of ionized calcium value < 0.94 mmol/L, < 1.05 mmol/L, and < 1.00 mmol/L being summarized. Blood pressure (systolic and diastolic) and heart rate will be summarized at each time point.

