**Time on study**

If the subject has ended study, time on study (in days) is defined as: time on study = end of study date – study Day 1 +1.

Otherwise, time on study (in days) = data cutoff day – study Day 1 +1, which is applicable for interim analysis only.

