**Study Day 1**

The date that the initial dose of IP is administered in Study 20140159. For subjects who didn't take any IP throughout the study, leave as missing.

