#### StudyBaseline Values

##### StudyBaselineatStudyDay1ofStudy20140159

Study Baseline iPTH, corrected total serum calcium, and serum phosphorus values are defined as the mean values of samples collected during the screening period and Study Day 1 pre-dose.

---

Product: Cinacalcet HCl  
Statistical Analysis Plan: 20140159  
Date: 24 May 2016

Page 13 of 36

---

Ca x P will be calculated at central lab COVANCE using corrected total serum calcium and serum phosphorus. **Study** Baseline value will be the mean of the values during the screening period and **Study** Day 1 pre-dose.

Study Baseline dry weight is defined as the value collected at **Study 20140159** Day 1 visit.

For all other variables, the **study** baseline value is defined as the last non-missing value collected prior to the first dose of IP, either during the screening phase or on Study Day 1.

All **study** baseline values will be calculated to the same number of decimal places as the raw data.

**Study**Baseline vitamin D use

Vitamin D use at **study** baseline is defined as any use of nutritional vitamin D or vitamin D sterol within 7 days prior to Study Day 1.

**Study**Baseline growth hormone use

Growth hormone use at **study** baseline is defined as any use of growth hormone during the screening period prior to Study Day 1.

**Study**Baseline phosphate binder use

Phosphate binder use at **study** baseline is defined as any use of any phosphate binder the day prior to Study Day 1.

**Study**Baseline calcium supplement use

Calcium supplement use at **study** baseline is defined as any use of any calcium supplement the day prior to Study Day 1.

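### SAP 10.7.2 gives the calcium-threshold counts no first-dose anchor and does not separate new lows from values already low at baseline, so entry rules alone can make the parent groups differ

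*SAP*

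**What the plan says.** Protocol 10.4.4 anchors the laboratory count to dosing: "The incidence of hypocalcemia after the first dose of IP will be summarized using descriptive statistics". It lists three corrected-calcium (cCa) limits (8.4, 8.0 and 7.5 mg/dL) and three ionized-calcium limits (1.05, 1.00 and 0.94 mmol/L).

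SAP 10.7.2 uses the same six limits ("Subject incidence of corrected total serum calcium value < 8.4 mg/dL, <8.0 mg/dL, <7.5 mg/dL or ionized calcium value < 1.05 mmol/L", and so on) but places the count "during study 20140159". It sets no condition on the baseline value. Laboratory results are shown by parent-study treatment and overall.

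Other definitions bear on the window:

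- SAP 6.2, Study Day 1: "The date that the initial dose of IP is administered in Study 20140159".
- SAP 6.1: "time on study = end of study date – study Day 1 +1".
- SAP 6.3: baseline cCa is "defined as the mean values of samples collected during the screening period and Study Day 1 pre-dose". For ionized calcium it is the last value before the first dose.

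Entry differs by parent group. Protocol 4.1.1 requires of former SOC children only: "Corrected calcium value ≥ 8.8 mg/dL within 7 days of day 1 in Study 20140159". It sets no calcium criterion for the cinacalcet arm of 20130356 or for children from 20110100. Protocol Section 4 adds that children from those groups "who had their dose withheld at the EOIP visit, may enroll in this study".

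**The concern.** Protocol Table 4 schedules cCa at screening and day 1, and ionized calcium on day 1. Sections 7.3.9 and 7.3.11 place these samples before dosing. For 20130356 children the end-of-product visit and extension day 1 are normally one visit, with shared samples applied to both studies. A low value produced by parent-study cinacalcet can therefore enter the extension table as a case. A child enrolled during a hold also has weekly ionized calcium checks before the first extension dose.

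Even with a clear post-dose window, a child who enters low and stays low looks the same as one who falls for the first time.

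Hypocalcemia is the central known risk: Protocol 2.4 describes a pediatric death with severe hypocalcemia in which a role of cinacalcet could not be excluded. The interim analysis for the pediatric sNDA uses extension data only, so this window governs its calcium-threshold rows. Two programmers could produce different tables from the present sentence.

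**Working it through.** **Planned size.** SAP 3.2 gives 48 from 20130356 and 30 from 20110100: 48 + 30 = 78, which reproduces the plan's figure. Protocol 2.5.1 randomizes the 48 in a 1:1 ratio, about 24 per arm. Pretreated children number at most 24 + 30 = 54, or 54/78 = 69%.

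**What each reading of the window admits**

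| Start of count | Screening values | Values during a hold before first dose | Day 1 pre-dose value |
|---|---|---|---|
| Protocol 10.4.4 (after first dose) | no | no | no |
| SAP, read from the first-dose date | no | no | not excluded |
| SAP, read from enrolment | not excluded if in study | yes | yes |

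**Effect on the count.** The documents give no rates, so every input here is an assumption: q, the share of pretreated children below 8.4 mg/dL before dosing; p, the rate of new lows after dosing; s, the share of entry-low children who stay low after dosing.

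- Literal count including pre-dose values: q + (1 − q)p
- Post-first-dose count with no baseline split: q[s + (1 − s)p] + (1 − q)p
- Count among children not low at baseline: p

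With p = 30%:

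| q | Literal count | Post-dose only, s = 0 to 1 | Not low at baseline |
|---|---|---|---|
| 5% | 33.5% | 30.0% to 33.5% | 30% |
| 10% | 37.0% | 30.0% to 37.0% | 30% |
| 20% | 44.0% | 30.0% to 44.0% | 30% |

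Restoring the protocol's anchor alone therefore does not isolate new cases.

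**Number of children.**

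- With a qualifying pre-dose value: 54 × 0.10 = 5.4 to 54 × 0.20 = 10.8.
- Net excess, since 30% would be counted anyway: 5.4 × 0.7 = 3.8 to 10.8 × 0.7 = 7.6. That is 7 to 14 percentage points of the 54, or 4.8 to 9.7 points of the 78.
- In general the excess in the pretreated group is q(1 − p). For q of 5% to 20% and p of 10% to 50% it runs from 0.05 × 0.5 = 2.5 points to 0.20 × 0.9 = 18 points.

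**Can former SOC children be low before dosing?** The 8.8 mg/dL criterion can be met by a screening sample, and day 1 is a separate draw. Treating the two as independent readings around the same level, P(day 1 cCa < 8.4) = Φ((8.4 − m)/(SD√2)), where m is the screening value. With an assumed within-child SD of 0.2 to 0.5 mg/dL this is 7.9% to 28.6% at m = 8.8, and 0.01% to 6.0% at m = 9.5. A low value is less likely for them, but possible.

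**The case against.** The strongest reply is that the SAP can be read as the protocol intends. Time on study starts on the first-dose date. The analysis windows map every calcium value at Study Day 1 or earlier to Baseline. The phrase sits under the extension-only heading, so it may serve only to separate extension from pooled data, and the SAP says that it implements the protocol. This stands as far as it goes: a reader might infer that the SAP deliberately counts pre-dose values, and the documents do not show that. The sentence still has no anchor, does not say that the visit windows govern it, and does not exclude the day 1 pre-dose draw.

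Second, dosing conditions shrink the affected group. The Safety Analysis Set requires a dose. Protocol 3.1.1 and 3.1.2 tie day 1 continuation to screening cCa, and children on hold must meet restart values first. This also stands: many held children should have recovered by their first dose. These are dosing conditions rather than inclusion criteria, however, and a recovered child's earlier low is still counted under the enrolment reading.

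Third, baseline is not absent from 10.7.2, which plans changes from study baseline and two-way CTCAE v3 shifts for both calcium measures. It would be wrong to say that the section ignores baseline. But the SAP does not tie those grades to the six limits.

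Fourth, the protocol's own definition has no baseline split, so adding one goes beyond restoring it. That is correct; the case for the split is the s = 1 end of the table above.

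**Conclusion.** The point holds as a window that departs from the protocol's wording and does not exclude pre-treatment values, together with threshold rows that mix new and carried-over lows. Because the cCa floor applies to one parent group only, these rows can differ between groups for reasons unrelated to extension treatment.

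The size is unknown. At most about 5 to 11 children would have a qualifying pre-dose value if 10-20% of 54 were low at entry. About 4 to 8 would be excess cases if 30% would become cases anyway. Both rates are assumptions, and the dosing conditions in Protocol 3.1.1 and 3.1.2 would lower the figures further.

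Two stronger readings are not supported. One is that former SOC children cannot be counted for a pre-dose value: they can, on a low day 1 sample after a qualifying screening value. The other is that entry is uneven for ionized calcium as well: Protocol 4.1.1 has no ionized-calcium criterion for any group, so the argument from inclusion criteria concerns cCa.

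The primary endpoint is defined separately, on adverse events from Study Day 1, and is unaffected. No test or sample size depends on these rows. The change should be made, but it is a reporting correction.

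**What to change.** In SAP 10.7.2:

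1. State that only calcium values taken after the first extension dose count, as Protocol 10.4.4 says, and that the day 1 pre-dose sample and all earlier values are excluded.
2. For each of the six limits, show by parent group and overall the incidence among children at or above that limit at study baseline, with children below it at baseline reported separately. The baselines in SAP 6.3 suffice. Because baseline cCa is a mean, say that the mean decides the classification even when one of its samples is below the limit.

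The cost is a few lines of SAP text and one extra column pair. Some cells will be small, so counts should be shown with their denominators. Study conduct does not change.

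Separately, the sponsor should reconcile Protocol 3.1.1 (screening cCa condition for continuing on day 1), 6.2.3.1.1 (day 1 conditions worded for all subjects but placed in the paragraph on a gap of more than one month) and Table 1 (a dose-decrease band at 8.0 to < 8.4 mg/dL). As written they leave unclear who may be dosed on day 1, and hence which low values can precede a first dose.
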